8.5.3 REPORTING UNANTICIPATED ADVERSE EVENTS TO PARTICIPANTS

Revance will disclose clinical trial data to individuals, to investigators at clinical sites, and publicly as aggregate summaries, in accordance to Regulatory and local legal requirements.

9 STATISTICAL CONSIDERATIONS

9.1 STATISTICAL HYPOTHESIS

Treatment with DaxibotulinumtoxinA for Injection of plantar fascia and plantar muscles combined with transient and selective partial paralysis of gastrocnemius/soleus complex (dysfunction) and a simple home program and inexpensive splinting will ameliorate signs and symptoms of plantar fasciitis; will improve function, and will optimize health related quality of life.

9.2 SAMPLE SIZE DETERMINATION

With a total of 60 subjects (30 per group) and assuming a drop-out rate of no more than 20%, [REDACTED]
[REDACTED]
[REDACTED]
[REDACTED]
[REDACTED]
[REDACTED]
[REDACTED]
[REDACTED]
[REDACTED]
[REDACTED]
[REDACTED]
[REDACTED]
[REDACTED]
[REDACTED]

9.3 POPULATIONS FOR ANALYSES

Approximately 60 subjects, 18-65 years of age, will be randomized in a 1:1 ratio to receive injections of either active (DaxibotulinumtoxinA for Injection) or placebo. [REDACTED]
[REDACTED]
[REDACTED]

9.4 STATISTICAL ANALYSES

9.4.1 GENERAL APPROACH

All evaluable efficacy data will be included in the analysis following the intent-to-treat (ITT) principle. All subjects who received the study treatment (DaxibotulinumtoxinA for Injection or placebo) will comprise the modified-ITT population and will be grouped according to each subject's randomization assignment. The primary analysis will focus on the reduction from baseline in the VAS for pain at eight (8) weeks with missing data imputed by the last available value prior to the visit with missing value, that is, the last-observation-carried-forward (LOCF) approach. Analysis of covariate (ANCOVA) model including treatment group as a factor and baseline pain score as a covariate will be used.

Reductions from baseline VAS for pain for the foot over time up to eight (8) weeks will also be analyzed using a statistical method that handles repeated measures such as a generalized linear model (GLM) including treatment group, time (visit) and the treatment-visit interaction term as factors and the baseline VAS for pain as a covariates. For other secondary and exploratory efficacy outcome measures, appropriate statistical models (e.g., ANCOVA or GLM for continuous variables, and chi-squared/Fisher's

exact test or logistic regression for dichotomy or categorical variables) adjusting for relevant covariates will be employed to evaluate the treatment effect.

As a sensitivity analysis to check the impact of major protocol violations to study results, the primary and secondary efficacy outcome measures will also be analyzed on data from all subjects in per-protocol (PP) population, which consists of subjects in the modified-ITT population who do not have any major protocol violations. To check the robustness of results using the LOCF approach, different methods (such as observed data only or multiple imputation) may be employed to handle missing data when appropriate.

As an exploratory analysis, proportion of subjects achieving certain status defined by some efficacy assessments (e.g., having a reduction in the VAS for pain by a certain clinical meaning cut-point) will also be compared between treatment groups.

Safety data from all subjects who received study treatment will be summarized with subjects being grouped based on the treatment each subject actually received.

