4.6.1.1 Primary Endpoint

The change from baseline in the VAS for pain for the affected foot at Week 8, in the ITT Population is the primary endpoint. [REDACTED]

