4.6.1.4 Sensitivity Analyses

As a sensitivity analysis to check the impact of major protocol violations on study results, the primary and secondary efficacy outcome measures will also be analyzed on observed data from all subjects in the per-protocol (PP) population. As well, to check the robustness of results using the LOCF approach, analysis using multiple-imputation for the missing data on ITT population

will be used as sensitivity analysis. Thus, each primary and secondary endpoint will have two additional sensitivity analyses.

[REDACTED]

[REDACTED]

[REDACTED]

[REDACTED]

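### LOCF as the primary Week 8 method can bias the treatment effect when pain is still changing, and no visible analysis departs from missing at random

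*Protocol*

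**What the plan says.** Protocol 9.4.1 takes the Week 8 reduction in VAS pain as the primary analysis, with "missing data imputed by the last available value prior to the visit with missing value, that is, the last-observation-carried-forward (LOCF) approach". The analysis of covariance is a "model including treatment group as a factor and baseline pain score as a covariate will be used". Protocol 9.4.2 leaves the full definition to the SAP. SAP 4.6.1.1 states that "The change from baseline in the VAS for pain for the affected foot at Week 8, in the ITT Population is the primary endpoint"; what follows is redacted. SAP 4.6.1.4 plans, "to check the robustness of results using the LOCF approach, analysis using multiple-imputation for the missing data on ITT population", so LOCF is still the method being checked. Its other sensitivity analysis uses observed data in the per-protocol population and is aimed at major protocol violations.

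Protocol 9.4.1 has two further elements. It allows observed-data or multiple-imputation checks at discretion. It also adds an analysis of VAS pain up to Week 8 by a method that "handles repeated measures such as a generalized linear model (GLM) including treatment group, time (visit) and the treatment-visit interaction term", with baseline VAS as covariate. No within-subject covariance structure is visible.

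Three other places matter:

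- The visits before Week 8 are Weeks 1, 2 and 4 (Protocol 8.1.2).
- Protocol 6.6.1 rules out rescue medication and says that subjects who require it may withdraw.
- Protocol 9.2 reads "With a total of 60 subjects (30 per group) and assuming a drop-out rate of no more than 20" percent. It gives no split by arm, and the rest is redacted.

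**The concern.** LOCF treats a score from Week 1, 2 or 4 as if it had been recorded at Week 8. That is harmless only if pain stops changing after the last observed visit. If both arms are still improving, each dropout is credited with too little improvement, and the arm that loses more subjects looks worse than it is. If the treatment effect is still growing, the active arm's dropouts lose more than placebo's, so the effect shrinks even when dropout is equal.

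Continued change is plausible. All subjects follow a standardized stretching and splinting program (Protocol 6.6), and entry depends on persistent pain, which invites regression to the mean. Pain-related withdrawal is plausible because of the rescue rule. At stake are the primary estimate and p-value in a trial with 30 subjects per arm.

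**Working it through.** **The plan's own figure.** Power, effect size, SD and alpha are redacted, so only the dropout arithmetic can be checked. 24 completers per arm / (1 − 0.20) = 30 per arm, or 60 in total. Up to 60 × 0.20 = 12 Week 8 values could therefore be filled in. Splits of 20/20, 30/10, 10/30 and 40/0 percent (placebo/active) all use those 12.

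**Formula for random dropout.** Let d be the dropout proportion in an arm (P placebo, A active), g the mean improvement still to come after the last observed visit, and Δ the true Week 8 difference. The LOCF mean of an arm is its true Week 8 mean minus d × g, so

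LOCF difference = Δ − d_A × g_A + d_P × g_P.

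Under the null, g_A = g_P = g, and the bias is (d_P − d_A) × g.

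**Assumed inputs** (not in the documents): two-sided alpha 0.05; last visit Week 1, 2 or 4 with equal chance; between-visit correlation 0.6.

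- Course A: improvement 8/13/19/25 mm at Weeks 1/2/4/8, SD 22 mm. g = 25 − (8 + 13 + 19)/3 = 11.7 mm. Null bias at 30/10: 0.20 × 11.7 = 2.3 mm.
- Course B: improvement 8/14/21/30 mm, SD 18/20/22/25 mm. g = 30 − (8 + 14 + 21)/3 = 15.7 mm. Null bias at 30/10: 0.20 × 15.7 = 3.1 mm.

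**Simulated LOCF-ANCOVA, 30 per arm, no true effect, random dropout:**

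| Course | Dropout P/A (%) | Bias, mm (+ toward active) | Two-sided type I error |
|---|---|---|---|
| A | 20/20 | about 0 | 4.9% |
| A | 15/5 | +1.1 | 4.8% |
| A | 25/15 | +1.2 | 5.9% |
| A | 30/10 | +2.3 | 6.2 to 6.9% (two separate runs) |
| B | 20/20 | 0.0 | 5.1% |
| B | 30/10 | +3.3 | 8.1% (7.3% favouring active) |
| B | 10/30 | −3.1 | 6.8% (0.4% favouring active) |
| B | 40/0 (extreme) | +6.2 | 14.7% |
| Flat | 30/10 | −0.1 | 5.0% |

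The course B and flat rows use 1,500 runs, so the Monte Carlo standard error is √(0.05 × 0.95/1500) = 0.6 points. Multiple imputation under MAR on the course B data had bias of 0.3 mm or less and type I error of 4.1 to 4.7%.

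**True effect of 15 mm at Week 8, random dropout.** At 20/20, LOCF gave 13.7 mm (course A) and 13.8 mm (course B). The course B figure implies g_A − g_P = (15 − 13.8)/0.20 = 6 mm, so g_A = 15.7 + 6 = 21.7 mm. The formula then gives:

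- 10/30: 15 − 0.30 × 21.7 + 0.10 × 15.7 = 10.1 mm (simulated 10.2).
- 30/10: 15 − 0.10 × 21.7 + 0.30 × 15.7 = 17.5 mm (simulated 17.8).

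Imputation under MAR gave 15.1, 14.9 and 15.1 mm at 20/20, 10/30 and 30/10.

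**Dropout related to outcome (course B, null, 30/10):**

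| Who leaves | LOCF | Imputation under MAR |
|---|---|---|
| Poor early responders | +3.0 mm, 4.8% (4.1% favouring active, nominal 2.5%) | 0.0 mm, 3.7% |
| Driven by unseen Week 8 pain | +1.1 mm, 4.7% | −4.4 mm, 13.5% |

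**The case against.** The strongest reply is that the harm is conditional and the conditions are assumed. The documents do not say that pain keeps falling in both arms, and these subjects had pain for over three months and had not responded to conservative treatment. A type I error of 6 to 8% needs a 3:1 dropout imbalance; at 25/15 or 15/5 it is 4.8 to 5.9%. The 20% may refer to Week 16 rather than Week 8. Protocol 7.2 asks for early-termination assessments, and Protocol 10.1.9.3 for data by telephone or mail, both of which reduce missing values. All of this stands and limits the size of the point. It does not remove the dilution under equal dropout, which needs only an effect that is still growing.

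A second reply also stands: MMRM relies on MAR too, and when dropout followed unseen Week 8 pain, imputation under MAR did worse than LOCF. Changing the primary method is therefore not enough without a check that departs from MAR.

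Three stronger readings are tempting but unsupported:

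- **LOCF favours the active arm.** It does so only if placebo loses more subjects; the reverse split works against active.
- **The sole missing-data check assumes MAR.** The visible SAP text gives no assumption for the imputation, the surrounding text is redacted, and Protocol 9.4.1 also offers an observed-data check and a repeated-measures model. What can be said is that none of these, as visible, departs from MAR.
- **The GLM treats visits as independent.** The protocol asks for a method that handles repeated measures, which contradicts that reading. The gap is an unstated covariance structure.

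**Conclusion.** The point holds in conditional form and should be fixed, although it does not invalidate the trial. LOCF-ANCOVA is the visible primary analysis. If pain is still changing after Weeks 1 to 4, 30%/10% random dropout biases a null comparison by about 2 to 3 mm and raises type I error to about 6 to 8%, toward whichever arm loses fewer subjects. A true 15 mm effect is reported as about 13.7 mm at 20/20 and about 10 mm at 10/30. With a flat course, or with equal random dropout and no effect, type I error stays near 5%.

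These sizes rest on assumed courses, SDs, correlation and dropout splits. Dropout before Week 1 was not simulated. Redacted SAP text could already contain part of the remedy.

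**What to change.** In Protocol 9.4.1 and SAP 4.6.1, make the repeated-measures analysis that is already planned the primary one. Specify it as an MMRM on observed changes at Weeks 1, 2, 4 and 8 with treatment, visit, treatment-by-visit, baseline VAS and baseline-by-visit, unstructured covariance and Kenward-Roger degrees of freedom. The treatment difference at Week 8 is the primary contrast. This replaces the generic GLM description.

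Keep LOCF-ANCOVA as a sensitivity analysis. State the assumption behind the planned multiple imputation, and add a delta-adjusted (tipping-point) version of it, because MMRM and standard imputation both rely on MAR and withdrawal for rescue may be driven by outcome. If redacted text already covers any of this, confirmation is enough for that part.

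The cost is protocol and SAP wording and a few lines of SAS; no new data are needed. The standard error changes slightly: for imputation under MAR it was between 4% smaller and 9% larger than for LOCF. Imputation stood in for the MMRM, which was not itself simulated.

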9.4.2 ANALYSIS OF THE PRIMARY EFFICACY ENDPOINT(S)

The primary endpoint is:

- Reduction in the visual analog scale (VAS) for pain for the foot at Week 8

Analysis of the primary efficacy endpoint is fully defined in the statistical analysis plan.

[REDACTED]

[REDACTED]

- [REDACTED]
- [REDACTED]
- [REDACTED]
- [REDACTED]

[REDACTED]

[REDACTED]

[REDACTED]

[REDACTED]

[REDACTED]

[REDACTED]

[REDACTED]

[REDACTED]

[REDACTED]

[REDACTED]

[REDACTED]

[REDACTED]

[REDACTED]

[Redacted]

[Redacted]

[Redacted]

[Redacted]

[Redacted]

[Redacted]

[Redacted]

[Redacted]

[Redacted]

[Redacted]

[Redacted]

[Redacted]

[Redacted]

[Redacted]

[Redacted]

[Redacted]

[Redacted]

[Redacted]

[Redacted]

[Redacted]

[Redacted]

[Redacted]

[Redacted]

[Redacted]

[Redacted]

[Redacted]

[Redacted]

[Redacted]

[Redacted]

[Redacted]

- [Redacted]

[Redacted]

10 SUPPORTING DOCUMENTATION AND OPERATIONAL CONSIDERATIONS

10.1 REGULATORY, ETHICAL, AND STUDY OVERSIGHT CONSIDERATIONS

10.1.1 INFORMED CONSENT PROCESS

10.1.1.1 INFORMED CONSENT AND AUTHORIZATION TO RELEASE HEALTH INFORMATION

Written informed consent will be obtained from all subjects before any study-related procedures (including any screening procedures) are performed. The Investigator may discuss the trial and the possibility for entry with a potential subject without first obtaining consent. However, a subject wishing to participate must give written informed consent prior to any study-related procedures being conducted, including those performed solely for the purpose of determining eligibility for study participation, and including withdrawal from current medication (if required prior to study entry). The Investigator has both the ethical and legal responsibility to ensure that each subject being considered for inclusion in this trial has been given a full explanation of the procedures and expectations for study participation.

The site-specific informed consent must be forwarded to Revance for approval prior to submission to an Institutional Review Board (IRB)/Independent Ethics Committee (IEC) that is registered with the US Department of Health and Human Services (HHS) or applicable health authority. Each subject will sign the consent form that has been approved by the same IRB/IEC that was responsible for protocol approval. Each informed consent document must adhere to the ethical principles stated in the Declaration of Helsinki and will include the elements required by FDA regulations in 21 CFR Part 50, as well as the elements required by the International Council for Harmonisation (ICH) Good Clinical Practice (GCP) guideline, and applicable federal and local regulatory requirements. The consent form must also include a statement that Revance, their designees, and auditing regulatory agencies will have direct access to the subject's records and medical history for study related purposes.

Once the appropriate essential information has been provided to the subject and fully explained by the Investigator (or a qualified designee) and it is felt that the subject understands the implications and risks of participating in the trial, the IRB/IEC approved consent document shall be signed and dated by both the subject and the person obtaining consent (Investigator or designee), and by any other parties required by the IRB/IEC or other regulatory authorities. The subject will be given a copy of the signed informed consent document with the original kept on file by the Investigator. All of the above activities must be completed before any study related procedures are conducted (including any screening study procedures).

10.1.1.2 CONSENT PROCEDURES AND DOCUMENTATION

Informed consent is a process that is initiated prior to the individual's agreeing to participate in the study and continues throughout the individual's study participation. Consent forms will be Institutional Review Board (IRB)-approved and the participant will be asked to read and review the document. The Investigator will explain the research study to the participant and answer any questions that may arise. A verbal explanation will be provided in terms suited to the participant's comprehension of the purposes, procedures, and potential risks of the study and of their rights as research participants. Participants will have the opportunity to carefully review the written consent form and ask questions prior to signing. The

participants should have the opportunity to discuss the study with their family or surrogates or think about it prior to agreeing to participate. The participant will sign the informed consent document prior to any procedures being done specifically for the study. Participants must be informed that participation is voluntary and that they may withdraw from the study at any time, without prejudice. A copy of the informed consent document will be given to the participants for their records. The informed consent process will be conducted and documented in the source document (including the date), and the form signed, before the participant undergoes any study-specific procedures. The rights and welfare of the participants will be protected by emphasizing to them that the quality of their medical care will not be adversely affected if they decline to participate in this study.]

10.1.2 STUDY DISCONTINUATION AND CLOSURE

This study may be temporarily suspended or prematurely terminated if there is sufficient reasonable cause. Written notification, documenting the reason for study suspension or termination, will be provided by the suspending or terminating party to study participants, investigators, the Investigational New Drug (IND) sponsor and regulatory authorities. If the study is prematurely terminated or suspended, the Principal Investigator (PI) will promptly inform study participants, the Institutional Review Board (IRB), and sponsor and will provide the reason(s) for the termination or suspension. Study participants will be contacted, as applicable, and be informed of changes to study visit schedule.

Circumstances that may warrant termination or suspension include, but are not limited to:

- Determination of unexpected, significant, or unacceptable risk to participants
- Demonstration of efficacy that would warrant stopping
- Insufficient compliance to protocol requirements
- Data that are not sufficiently complete and/or evaluable
- Determination that the primary endpoint has been met
- Determination of futility

Study may resume once concerns about safety, protocol compliance, and data quality are addressed, and satisfy the sponsor, IRB and/or Food and Drug Administration (FDA).

[REDACTED]

[REDACTED]

[REDACTED]

[REDACTED]

| | |
|------------|------------|
| [REDACTED] | [REDACTED] |
| [REDACTED] | [REDACTED] |
| [REDACTED] | [REDACTED] |
| [REDACTED] | [REDACTED] |
| [REDACTED] | [REDACTED] |
| [REDACTED] | [REDACTED] |
| [REDACTED] | [REDACTED] |

10.1.6 SAFETY MONITORING/DATA MANAGEMENT COMMITTEE

An independent Data Management Committee (DMC) will be appointed to review safety data during the study. Details of the composition and scope of the committee’s mandate will be presented in a DMC Charter document. Following recruitment of all subjects, the DMC will evaluate all safety data available at timepoints specified in the Charter, and will make appropriate recommendations.

10.1.7 MONITORING, COMPLIANCE, AND QUALITY

All aspects of the trial will be monitored by Revance or authorized representatives of Revance according to Good Clinical Practices (GCP) and Standard Operating Procedures (SOPs) for compliance with applicable government regulations, (i.e., Informed Consent Regulations and Institutional Review Board regulations).

[REDACTED]

[REDACTED]

[REDACTED]

10.1.9 DATA HANDLING AND RECORD KEEPING

10.1.9.1 DATA COLLECTION AND MANAGEMENT RESPONSIBILITIES

10.1.9.1.1 DATA COLLECTION

For this trial, all protocol-specified data recorded in the source documents will be entered on the CRFs from the source documents. Subject assessments will be completed by the individual subjects directly on the corresponding CRFs. In addition to signature confirmation that a subject meets the study eligibility criteria, upon each subject’s completion of the trial, the Investigator will sign a statement indicating that all pages of the subject’s case report have been reviewed. Signature stamps and “per signatures” are not acceptable.

It is Revance’s policy that the trial data be verifiable with the source data that necessitates access to all original recordings, laboratory reports, and other records for each subject. The Investigator must therefore

agree to allow access to subjects' records, and source data must be made available for all trial data. Subjects (or their legal representatives) must also allow access to their medical records. Subjects will be informed of the importance of increased record access and permission granted by signature on the informed consent document prior to Screening.

Checks will be performed to ensure the quality, consistency, and completeness of the data. Instances of missing or un-interpretable data will be resolved with the Investigator or Study Coordinator. Data queries will be sent to the trial center. Site personnel will be responsible for providing resolutions to the data queries and for correcting the CRFs, as appropriate. All unused Revance source documents and binders must be returned to Revance upon completion of the trial.

The Investigator must keep written or electronic source documents for every subject participating in the clinical trial. The subject file that identifies the study in which the subject is participating must include the subject's available demographic and medical information including:

- Date of birth
- Sex
- Race
- Ethnicity
- Medical history
- Comorbid conditions
- Concomitant therapies/medication
- Study visit dates
- Performed examinations, evaluations, and clinical findings
- Investigational product administration
- AEs, SAEs, or pregnancy (as applicable)

Additionally, any other documents with source data, especially original printouts of data that were generated by technical equipment must be included in the subject's source document (e.g., laboratory value listings). All these documents must have at least the subject's initials, trial number, and the date of the evaluation.

The data recorded during the course of the trial will be documented in the CRF and/or the trial-specific forms. Before or at study termination, all data must be forwarded to Revance. The data will then be recorded, evaluated, and stored in anonymous form in accordance with data-protection regulations.

Subjects will authorize the use of their protected health information during the informed consent process in accordance with the applicable privacy requirements. Subjects who deny permission to use and disclose protected health information will not be eligible to participate in the trial. The Investigator will ensure that the trial documents forwarded to Revance, and any other documents, contain no mention of subject names.

Any amendments and corrections necessary will be undertaken in both the source documents and CRFs (as appropriate) and countersigned by the Investigator, or documented designee, stating the date of the amendment/correction. Errors must remain legible and may not be deleted with correction aids. The

Investigator must state his/her reason for the correction of any data. In the case of missing data/remarks, the entry spaces provided in the CRF should be cancelled out so as to avoid unnecessary follow-up inquiries.

Regulatory authorities, the IRB/IEC and/or the Revance's Quality Assurance group (or designee) may request access to all source documents, CRFs, and other trial documentation for on-site audit or inspection. The Investigator must guarantee direct access to these documents. CRFs will be kept by Revance or an authorized designee in a secured area. Clinical data will be recorded in a computer format for subsequent statistical analyses. Data files will be stored on electronic media with a final master data file kept by Revance after descriptive and statistical analyses and reports have been generated and are complete.

